### 3.2 Population-based studies:

In addition to the prospective study, we intend to include retrospective data from a population-based study with echocardiography from Katholieke Universiteit Leuven, Belgium. This study has already been approved for baseline echocardiography and follow-up assessment. Participants with LBBB or PVP of the Tromsø 7 study will be invited to be prospectively included into the study-population from University Hospital of North Norway, Tromsø .

### 3.3 Planned inclusion of participants of Tromsø 7

The main focus of this study is to identify individuals with LBBB or ventricular pacing who have characteristics for stable disease or those who are soon developing clinical heart failure.

Asymptomatic Individuals with LBBB are usually not referred to the cardiologist. In order to create a suitable control-algorithm for these stable diseases and to identify individuals who present with subclinical heart failure who are in need of either medical treatment or even CRT it will be important to include the broad spectra of patients and "healthy" participants of epidemiological studies. ECG of the participants of Tromsø 7 have been analyzed and we wish to include all participants with increased QRS width >130ms and LBBB configuration or predominant ventricular pacing, excluding those with

RBBB configuration. Echocardiography in individuals with LBBB and predominant ventricular pacing is clinically indicated.

### 3.4 Primary outcome

Deterioration, stability or improvement of markers for myocardial function over time. Outcome-variables will be measured by deterioration or non-deterioration of LV function by defining deterioration of ventricular function by using either echocardiographic parameters that are classically used for the definition of CRT responders: EF decrease by >5% with EF initially <55% or >10% with EF initially  $\geq$  55%, LV diastolic or systolic volume enlargement by 10%, NYHA class deterioration or proBNP increase by >10%.

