## 3 Project arrangements, method selection and analyses

### 3.1 Patients

This is a longitudinal prospective cohort-study intending to include at least 1000 patients with LBBB from University Hospital of North Norway Tromsø and Harstad, Akershus University Hospital, Lørenskog, Oslo University Hospital, Rikshospitalet, Haukeland University Hospital, Bergen and Nordlands Hospital, Bodø, over a 2-year inclusion period.

Information about present and previous diseases, medication, surgical- or invasive treatment, PM, ICD or CRT implantation, clinical examination and present and previous echocardiographic imaging and blood samples (Hb, Thrombocytes, CRP, Kreatinine, eGFR, Urate, HbA1C, Cholesterol, ProBNP, Troponins, ALAT and Ferritin) will be accessed by the patient's journal.

All prospective study participants will answer one customized and two standardized (EQ5D and HeartQoL) questionnaires. They will undergo general clinical investigation comprising height and weight measurements, baseline ECG, blood samples when not found in the patient's journal, standardized BP measurements and echocardiography with a 3 minutes- hand-grip test at baseline and in a 18 month follow-up study.

Clinical outcome data including death and hospital admissions due to heart failure and CRT implantation will be assessed after 3 and 5 years (eventually after 10 and 15 years) by linkage to data from the patient's clinical records through access to Norwegian Patient Registry (Norsk pasientregister (NPR)), Norwegian Causes of Death Registry (Dødsårsaksregisteret) and Norwegian Cardiovascular Disease Registry (Hjerte- og karregisteret).

St Olavs Hospital, Trondheim, might provide retrospective patient data with echocardiography loops, where outcome-data will be extracted from the same registries.

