### 3.5 Secondary outcomes

Hospital admissions, adverse cardiovascular events, mortality, CRT implantation and initiation of medical treatment for heart failure.

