### 3.7 Exclusion criteria

Typical RBBB. No ability to give informed consent, non-cardiovascular co-morbidities with reduced life-expectancy < 1 year or patients with complex congenital heart disease.

In-hospital patients will be included during the in-hospital period and the baseline echocardiogram and BP monitoring will be performed as part of the routine clinical investigations. From the “Out-patients’ clinics the patients will be recruited after assessing ECGs from patient’s records.

In a Pilot-study feasibility of patient recruitment will be tested. The incidence of heart failure and deterioration of ventricular function in the first 100 included patients will be assessed in order to define the power of the final study-population size.

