### 3.10 Statistical power

It is unknown how high the percentage in this study population will be who suffer from deterioration of LV function. Therefore, a pilot-study on the first 100 study-subject of the different subgroups will be performed in order to calculate the power of the final population size. Pilot participants will be included into the final study population. Assuming different proportions of 5%, 10%, 20% and 30% of patients with deteriorating ventricular function, a difference in septal or global strain between at 5% at a SD of  $\pm 6\%$  the sample size needed for hypothesis 1 in each subgroup will be 220, 129, 73 or 57, respectively for a two-sided test and a Type I error of 0.05.

For calculation of hazard-ratios between patients with against without deterioration of LV function for the primary outcome variable: hospital admission due to CVD, assumed that 5% of all patients either

deteriorate function and the presence of decreased segmental work indicates at least a relative risk of 1.8, at an alpha of 0.05 with 500 patients included, the statistical power will be 82%.

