### 3.11 Statistics

Patients with deteriorating myocardial function will be identified by increasing proBNP by more than 10%, increasing NYHA class, increasing diastolic volume by more than 10% and/or decreasing EF by more than 5%. ANOVA will be used to compare parameters between patients with deteriorating myocardial function and those with unchanged clinical condition after one year. ROC curve analysis will serve to find the ideal cut-off values for continuous variables and assessing sensitivity and specificity of the tests. Univariate and multivariate logistic regression tests will be performed in order to identify the most powerful parameters predicting development of heart-failure with hospital admissions as primary outcome and predicting death (or transplantation) as secondary outcome.

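### Sections 3.4 and 3.5 make LV deterioration primary and hospital admissions secondary, section 3.10 calls admission primary, and the definition and timing of LV deterioration also differ between sections

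*Protocol*

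**What the plan says.** - **Outcome sections.** Section 3.4 names "Deterioration, stability or improvement of markers for myocardial function over time" as primary and defines deterioration of LV function. Section 3.5 lists as secondary: "Hospital admissions, adverse cardiovascular events, mortality, CRT implantation and initiation of medical treatment for heart failure".
- **Power section, first calculation (3.10).** It sizes a strain difference between patients with and without deteriorating function: "the sample size needed for hypothesis 1 in each subgroup will be 220, 129, 73 or 57", for assumed deterioration in 5%, 10%, 20% or 30%.
- **Power section, second calculation (3.10).** It concerns hazard ratios between patients with and without LV deterioration for "the primary outcome variable: hospital admission due to CVD", and states 82% power with 500 patients, a relative risk of 1.8 and alpha 0.05.
- **Statistics section (3.11).** The regressions are aimed at "predicting development of heart-failure with hospital admissions as primary outcome and predicting death (or transplantation) as secondary outcome". The same section defines deterioration again, with criteria that differ from 3.4.
- **Hypotheses and objectives.** Primary hypothesis 1 (2.1) and primary objective 1 (2.3) each list several outcomes without ranking them.
- **Timing.** Section 3.1 puts the repeat examination at 18 months. Sections 1, 2.4, 3.11 and 4 put it at one year. For the registry data, 3.1 says "hospital admissions due to heart failure and CRT implantation will be assessed after 3 and 5 years".

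**The concern.** The same event is secondary in one section and primary in another, and the outcome that 3.4 calls primary becomes the exposure in 3.10. A reader cannot tell from the protocol which result the study stands or falls on, when it is read out, or which size calculation belongs to it.

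Settling the label would not settle everything. The outcome in 3.4 also has two definitions and two measurement times, so if LV deterioration is meant to be primary, the protocol does not yet define it uniquely.

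**Working it through.** **1. The label.**
- 3.4: LV deterioration is primary.
- 3.5: hospital admissions are secondary.
- 3.10, second calculation: admission due to CVD is primary and LV deterioration is the grouping variable.
- 3.11: admission is called primary, but that word may only rank the regressions among themselves.
- 2.1 and 2.3: unranked lists.

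The unambiguous contradiction is 3.10 against 3.4 and 3.5. No section ranks one above another.

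**2. The two calculations in 3.10.**
- *Strain difference.* Inputs from 3.10: difference 5, SD 6, two-sided 0.05. Power is not stated; I assume 80%. Total N = (6/5)² × (1.96 + 0.84)² / [p(1 − p)] gives 238, 126, 71 and 54 for p = 5%, 10%, 20% and 30%. The protocol has 220, 129, 73 and 57, which is close except at 5%, where 220 gives about 76.5% power.
- *Admission.* Power = Φ(ln 1.8 × √[d × p(1 − p)] − 1.96), with d events and exposed share p. With d = 500 and p = 0.05: √23.75 = 4.873; 4.873 × 0.588 = 2.86; 2.86 − 1.96 = 0.90; power 81.7%. This matches the stated 82%, but only if all 500 patients are admitted.
- *Another route to 81.7%.* Treat 5% as the event rate and 1.8 as an effect per SD of a continuous predictor. That does not fit an exposure described as present or absent.
- *What is missing.* 3.10 gives no admission rate, and it mentions both LV deterioration and decreased segmental work as the exposure. If 10%, 20% or 50% of 500 patients were admitted (my assumption) with 5% exposed, the formula gives about 15%, 25% or 53%. These figures show that the 82% cannot be read without a rate; they do not estimate the study's power.

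**3. The definition of deterioration.**
- 3.4: EF fall above 5% if baseline EF is below 55%, above 10% otherwise; diastolic or systolic volume up by 10%.
- 3.11: EF fall above 5% for everyone; diastolic volume only, up by more than 10%.
- Both also use NYHA class and proBNP, held unchanged here. I take any single criterion as sufficient.

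EF = (diastolic − systolic) / diastolic. The volumes are illustrative.
- *120/42 to 110/45 mL.* EF 78/120 = 65.0% to 65/110 = 59.1%: a fall of 5.9 points or 9.1% relative. Diastolic −8.3%, systolic +7.1%. Deteriorated under 3.11 only.
- *120/42 to 126/47 mL.* EF 65.0% to 79/126 = 62.7%: a fall of 2.3 points or 3.5% relative. Diastolic +5.0%, systolic +11.9%. Deteriorated under 3.4 only.

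Both results hold whether EF change is read in points or as a relative change. The protocol does not say which.

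**4. The timing.** The repeat visit is at 12 months (sections 1, 2.4, 3.11, 4) or 18 months (3.1). The first linkage is at 3 years. LV status is therefore known 3 − 1.5 = 1.5 to 3 − 1 = 2 years before the first admission data.

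**The case against.** The section headed as the primary outcome is clear, and the firm contradiction is one label in one awkward sentence of 3.10. This is an observational cohort without a stated test hierarchy, and a SAP that is not shown may settle the matter. Section 3.11 already compares deteriorating with unchanged patients by ANOVA and plans ROC analysis. Section 3.12 blinds strain readers to outcome data.

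Much of this limits the consequences, but the contradiction stands: a SAP that chose one outcome would still conflict with a section of the protocol, and blinded reading does not decide which outcome is primary.

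Several stronger readings are tempting and are not supported:
- *The pilot leaves open which outcome drives the size.* Section 3.7 does say "The incidence of heart failure and deterioration of ventricular function in the first 100 included patients will be assessed", but 3.10 names LV deterioration alone as the unknown behind the pilot. The pilot looks at incidence; no test of predictors against outcome is described, so a selective look is not shown.
- *The study is too small.* Section 3.1 is "intending to include at least 1000 patients with LBBB", which exceeds 500, and the final size awaits the pilot.
- *The false-positive rate is inflated by a known amount.* The protocol fixes neither the number of tests nor their dependence, so no figure follows.
- *Admission has four competing definitions.* Sections 3.1 and 3.5 describe data and list outcomes; they do not define an endpoint. The differing wording is a minor alignment point.

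**Conclusion.** The protocol is wrong as written on its primary outcome. Sections 3.4 and 3.5 contradict 3.10 and nothing resolves it, so the primary result and its read-out (12 or 18 months against 3 and 5 years) are not fixed in advance. Two calculations, 220/129/73/57 per subgroup and 500 patients at 82%, attach to different outcomes.

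The definition in 3.4 conflicts with 3.11 in both directions, and the repeat-visit time conflicts between 3.1 and four other sections. How many patients would change class cannot be derived from the document. The two examples show that disagreement is possible, not how common it is, and they assume that one criterion suffices.

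The textual conflict needs no numerical assumption. The remark on the 82% rests only on the absence of an admission rate in 3.10.

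**What to change.** Before follow-up outcome data are analysed, name one primary outcome, use it in 3.4, 3.5, 3.10 and 3.11, and label the other secondary. The headings of 3.4 and 3.5 favour LV deterioration; the sponsor decides.

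- *If LV deterioration is primary:* relabel admission as secondary in 3.10 and 3.11, and state that the prediction models of 3.11 also cover LV deterioration. As worded they cover heart failure with admissions, and death.
- *If admission is primary:* move it to 3.4 with one event definition and a read-out time.
- *In either case:* restate the 82% with its assumed admission rate and a single named exposure, since relabelling alone does not repair that paragraph. Use one deterioration definition in 3.4 and 3.11 and say whether EF change is in points or relative. Reconcile the repeat-visit time across sections 1, 2.4, 3.1, 3.11 and 4. Align the admission wording.

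The cost is protocol wording, one restated power calculation and, under the first option, one further model on data already planned. No new data collection is needed.

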### 3.5 Secondary outcomes

Hospital admissions, adverse cardiovascular events, mortality, CRT implantation and initiation of medical treatment for heart failure.

### 3.6 Inclusion criteria

Patients with typical LBBB, thus QRS complex >130 ms and R-wave duration in V6 >70 ms or atypical LBBB or patients with predominantly ventricular pacing will be included. Atypical LBBB is present, when the Minnesota code criteria for typical LBBB are not met, at a QRS of >130ms and the absence of right bundle branch block (RBBB). Several subgroups will be defined as follows: 1. PM dependent patients with ventricular pacing over 50% including new implanted PM with AV block grade 3 or in need of heavy rate reduction (His bundle ablation), 2. Bundle branch block following acute myocardial infarction. 3. Baseline investigation of patients with CRT indication will be performed shortly before CRT implantation. In case of already implanted CRT, in addition to the inclusion to the prospective study, previous echocardiograms will be retrospectively analyzed for strain-patterns, ventricular geometric properties and clinical assessment from the patient's records. Patients with HBP will be included as a control-group.

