### 1.5 “Novel echocardiographic indices”

Modern echocardiographic modalities like segmental strain imaging allows to visualize and quantify the typical early shortening of the septum followed by the delayed contraction of the lateral wall (10). This pattern has an important prognostic value in patients with established heart failure as its absence was shown to be associated with unfavorable outcome after CRT implantation with increased risk of death or transplantation (40). Computer models could show that the typical strain-patterns changed in dependence on global regional contractility of the septum and lateral wall.

Patients responded to CRT treatment when typical patterns for electro-mechanical dyssynchrony were present. These patterns can be quantitatively assessed by newly developed algorithms (42). In addition to qualitative and quantitative strain-curve analysis “LV workload quantification” and “analysis of energy loss and waste of myocardial work” have been recently introduced as new echocardiographic measures(43) also applicable in the presence of dyssynchrony (12). These are based on strain imaging combined with BP measurements, where strain loop areas can be derived. It has been demonstrated that

contraction of the septum in patients with LBBB and chronic heart failure perform a net negative work (systolic lengthening) while after CRT positive work (systolic shortening) increases dramatically (11). In small patient populations myocardial work showed to be a good indicator for CRT response(44).

**Figure 2:** Pressure strain curves in simulations with narrow QRS complex and with LBBB, and changes with afterload. The area under the curve expresses segmental myocardial work in the septum (upper row) and lateral wall (lower row) (F.Prinzen, E.Willem, J. Lumens JACC-CVI 2019)

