### **2.2 Secondary hypotheses**

1. Patients with high afterload have typical dyssynchrony patterns with earlier deterioration of cardiac function over time.
2. Repetition of echocardiographic assessment and clinical parameters increases accuracies of outcome-prediction.
3. Predictors for major adverse cardiovascular and cerebrovascular events (MACCE) indicate also CRT- or medical treatment- response. These factors might be useful indicators for risk reduction through treatment of carefully selected patient-groups
4. Patients showing ability to increase or sustain myocardial work during a stress test with no classic pattern of dyssynchrony have a good long-term prognosis.
5. HBP can prevent development of heart failure compared to usual ventricular pacing.

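### Section 3.11 does not separate CRT-treated from untreated patients in the deterioration comparison, although the protocol expects the dyssynchrony marker to point in different directions in the two

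*Protocol*

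**What the plan says.** **Who is enrolled.** Section 3.6 of the Protocol lists patients with a CRT indication among its subgroups: "Several subgroups will be defined as follows", and for the third, "Baseline investigation of patients with CRT indication will be performed shortly before CRT implantation". Patients with a device in place also enter: "In case of already implanted CRT, in addition to the inclusion to the prospective study, previous echocardiograms will be retrospectively analyzed for strain-patterns". Section 3.7 excludes neither group.

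**What the marker means under CRT.** Section 1.5: "Patients responded to CRT treatment when typical patterns for electro-mechanical dyssynchrony were present". Of the same pattern it says that "its absence was shown to be associated with unfavorable outcome after CRT implantation with increased risk of death or transplantation".

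**What the marker means without CRT.** Secondary hypothesis 1 in section 2.2 links high afterload to "typical dyssynchrony patterns with earlier deterioration of cardiac function over time". Secondary hypothesis 4 expects a good long-term prognosis in patients who keep up myocardial work under stress and lack the classic pattern.

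**How it is analysed.** Section 3.4 divides patients into deteriorated and not deteriorated. Section 3.11 says "ANOVA will be used to compare parameters between patients with deteriorating myocardial function" and those whose condition is unchanged, followed by ROC analysis and logistic regression. CRT is not mentioned in 3.11. In section 3.5 it appears only as a secondary outcome: "CRT implantation and initiation of medical treatment for heart failure".

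**The concern.** Primary objective 1 is to find patients whose myocardial function will deteriorate, so that CRT can be timely. That is a question about the course without CRT. If treated patients sit in the same comparison and the marker works differently in them, the estimate is a mixture of two associations and answers neither the natural-history question nor the CRT-response question. A real marker effect could be missed, or reported as much smaller than it is.

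Implantation between the two echoes adds a second problem. A patient who declines, is implanted and recovers can be coded as not deteriorated. Because the study looks for patients heading towards CRT, those who decline are also likely to be implanted, so this misclassification is not random.

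**Working it through.** **1. The plan's own figures.** Section 3.10 sizes hypothesis 1 per subgroup from a strain difference of 5 with SD 6, two-sided alpha 0.05. Power is not stated; I take 80%. With a proportion p deteriorating,

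N = (6/5)² × (1.960 + 0.842)² / [p(1 − p)] = 11.30 / [p(1 − p)].

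| p | Stated N | Normal formula | Noncentral t |
|---|---|---|---|
| 5% | 220 | 238 | 240 |
| 10% | 129 | 126 | 128 |
| 20% | 73 | 71 | 73 |
| 30% | 57 | 54 | 56 |

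The last three agree to within a patient with the t version. The first does not (220 gives about 77% power); that is a separate matter.

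**2. Dilution on the strain scale.** Let f be the share of patients on CRT. The protocol does not give it, so it is varied. Suppose the difference is exactly reversed under CRT and the two groups are otherwise alike. The pooled difference is then 5(1 − f) − 5f = 5(1 − 2f), and power is Φ{[5(1 − 2f)/6] × √[N p(1 − p)] − 1.96}. For N = 129, p = 10%: √11.61 = 3.407. At f = 0, 0.833 × 3.407 − 1.96 = 0.88, power 81%. At f = 20%, 0.5 × 3.407 − 1.96 = −0.26, power 40%.

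| f | Pooled difference | Power over the four stated N |
|---|---|---|
| 0 | 5 | 77–82% |
| 10% | 4 | 58–64% |
| 20% | 3 | 37–41% |
| 30% | 2 | 19–21% |
| 40% | 1 | 8% |
| 50% | 0 | none |

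The difference reaches zero only at f = 50% with an exactly equal and opposite effect.

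**3. Dilution on the odds-ratio scale, with selection.** I simulated 400,000 patients with a standard normal marker. The log-odds of CRT rise by 0.5 per SD of marker. The log-odds of deterioration rise by ln 1.8 per SD without CRT; under CRT the slope is either −ln 1.8 (reversal) or 0 (association removed). CRT has no main effect. Intercept risk is 5%, 10% or 20%. A logistic model with the marker alone is then fitted. Information kept is (ln pooled OR / ln 1.8)².

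| CRT share | Pooled OR, reversal | Information kept | Pooled OR, removed | Information kept |
|---|---|---|---|---|
| 12% | 1.54–1.55 | 53–56% | 1.64–1.65 | 71–72% |
| 22% | 1.36–1.38 | 27–29% | 1.54 | 54% |
| 32% | 1.22–1.23 | 11–12% | 1.45 | 40% |
| 41% | 1.10–1.11 | 3% | 1.38 | 30% |

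Ranges are over the three intercept risks. The 1.8 is borrowed as a size only: in section 3.10 it is a relative risk for decreased segmental work, with cardiovascular admission as the outcome.

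**4. Who is in the comparator.** Under section 3.4 an improved CRT responder is a non-deteriorator and stays in the reference group. Under section 3.11 the reference group is unchanged patients, so the same responder may drop out. The two sections give different samples, and the bias from CRT differs between them.

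**The case against.** **A reader might infer that the plan pools CRT and untreated patients.** It does not say so. CRT-indicated patients are a named subgroup, section 3.10 sizes hypothesis 1 for each subgroup, and secondary objective 3 compares risk indicators with indicators of CRT response. A statistical analysis plan that is not shown may separate them. This stands as far as it goes: pooling is a reading of 3.11, not a statement in it. But 3.11 sets out the main comparison and does not carry the subgroups into it. Nor would baseline subgroups be enough: a paced or post-infarction patient implanted after baseline stays in the original group, and an LBBB patient in none of the listed subgroups does not join the CRT one.

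**A reader might infer that the association cancels.** It does not, short of about half the cohort on CRT with exact reversal. Dilution is what the documents support.

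**The opposite directions are less firm than they look.** Secondary hypothesis 1 is about patients with high afterload, and the section 1.5 evidence concerns response, death or transplantation in established heart failure. Nothing in the protocol implies an equal and opposite slope for deterioration. This also stands, which is why the milder case, where CRT only removes the association, is shown beside the reversal.

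**Conclusion.** The point holds as a gap in section 3.11 that should be closed before outcomes are analysed. The protocol's own expectations make CRT status a modifier of the marker's meaning, and the stated comparison ignores it. A comparison run as written would be diluted: from an odds ratio of 1.8 to about 1.5–1.1 under reversal, or about 1.64–1.38 if CRT only removes the association, at CRT shares of roughly 12% to 41%.

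These sizes rest on assumed CRT shares, a borrowed effect size, moderate selection into CRT by the marker and no CRT main effect. The direction needs less: only that the marker's adverse association is weaker or reversed under CRT. That the repeat echo after an intervening implantation no longer shows the untreated course does not depend on any of these figures.

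**What to change.** In section 3.11:

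1. Run the natural-history deterioration analysis in patients with neither CRT nor a planned implantation at baseline.
2. Analyse CRT patients separately for CRT response, or fit one model with a marker-by-CRT interaction and report the association by CRT status.
3. For implantation between the two echoes, count implantation as deterioration (a composite) in one analysis, and exclude or censor these patients in a sensitivity analysis. Do not carry forward pre-CRT values as the main rule. Only one repeat study echo is planned, so unless the records hold a later pre-implantation echo the last values are the baseline ones; change is then zero and patients who worsened enough to be implanted count as stable.
4. Reconcile sections 3.4 and 3.11 on whether improved patients belong in the comparator.

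No new data are needed, since CRT status and implantation are already to be recorded. The cost is a smaller natural-history sample, so the pilot-based sample-size review should count only the patients who qualify for that analysis.
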